4.2 Exclusion Criteria

All candidates meeting any of the following exclusion criteria at baseline will be excluded from study participation.

- 1) Uncontrolled diabetes mellitus (HBA1c >10%)
- 2) History of stroke, dementia or clinically impaired gait (Mini-mental status exam score (MMSE) <24, Short Physical Performance Battery for gait (SPPB) < 9,)
- 3) Body Mass Index > 45 kg/m² and/or arm circumference > 44 cm)
- 4) Poor kidney function (defined as estimated GFR <30 ml/minute)
- 5) Active liver disease or serum transaminases >3 times the upper limit of normal
- 6) Major cardiovascular event (e.g. myocardial infarction) or procedure (e.g. cardiac bypass surgery) in past 3 months; stroke with residual gait abnormality
- 7) Uncompensated congestive heart failure (NYHA class III or IV or documented ejection fraction <30%)
- 8) Chronic atrial fibrillation that disallows ambulatory BP monitoring to be successfully performed
- 9) Medical conditions that limit survival to < 3 years
- 10) Non-dermatologic cancer diagnosed within 2 years
- 11) Organ transplantation requiring anti-rejection drug therapy
- 12) Severe and unexplained weight loss (>15%) in past 6 months
- 13) Medical need to undergo recurrent phlebotomy or blood transfusions
- 14) Current participation in another investigational trial
- 15) Unable to obtain informed consent

- 16) Factors limiting adherence to the interventions
- 17) MRI contraindications (including MRI-incompatible implants, severe claustrophobia).
- 18) Known carotid or intracranial arterial occlusive disease.

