4.3 Study Enrollment Procedures at University of Connecticut Health Center

Study recruitment and enrollment. The study is a single-site randomized clinical trial that will be performed at the University of Connecticut Clinical Research Unit. Patients will be recruited from a variety of sources as described below. Three hundred patients will be enrolled into the trial in order to randomize 200 patients and complete 140 patients at 3 years of randomized treatment. Based on our prior experience in studying patients in this age group with hypertension and mild mobility issues, we project a 3-year attrition rate of approximately 30%. Recruitment will be carried out by several mechanisms, including: A) contacting former research participants from the Cardiology and Hypertension faculty practices, the Center on Aging, and Neurology who have agreed to be informed of future studies, B) publically posted advertisements in addition to advertisements on the internet, radio and newspapers, C) Recruitment presentations conducted at community health centers, faith-based organizations and senior centers in conjunction with BP community clinics.

Recruitment will be extended into the greater Hartford region to improve minority participation. Advertisements will state that we are seeking volunteers for a treatment study aimed at older patients with hypertension willing to join a study involving the evaluation and treatment of high blood pressure, mobility and cognitive function. The

ads will state that antihypertensive medication, clinical visits, brain imaging, and other testing will be provided at no cost.

Following voluntary assent, interested individuals will be screened by phone for inclusion/exclusion criteria. Those meeting initial screening criteria will be invited to a Consent/Evaluation Visit during which informed consent will be obtained, followed by a medical history, physical exam, and tests to determine eligibility. Those not meeting study criteria will be referred for medical care. Patients not able to read and understand the consent form will be excluded from the study.

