Here, x_i is the treatment group indicator for participant i as in (1); Y_{i1} is the mobility score for participant i at time 1 (baseline); Y_{i2} is the mobility score for participant i at time 2 (36 month follow-up); β_0 is interpreted as the average mobility score at baseline in the reference group; β_C is interpreted as the difference in the average mobility score at baseline between the intervention group and the reference group and will be zero if the two groups are exactly comparable in their baseline values; β_L is interpreted as the average change in mobility between 36 month follow up and baseline in the reference group; β_T is interpreted as the difference average change in mobility between 36 month follow up and baseline between the intervention group and the reference group and thus the parameter of primary interest; γ_i is a random intercept for participant i that addresses the correlation in mobility across the two time points; and ε_{i1} and ε_{i2} are the residual error terms at baseline and follow-up, respectively.

This analysis will be repeated for each mobility parameter (gait speed, four stair ascent and descent time, supine to sit time), cognition scores (Trailmaking A and B, Stroop Color & Word score, and simple reaction time), and the Geriatric Depression Scale. The timed measures – Trailmaking A and B, and simple reaction time – will be inverse-transformed so that they have a speed interpretation; this will also reduce the influence of outliers. Similarly, all analyses will be repeated as stratified analyses (b - e below).

- b. Stratified according to < or > median age
- c. Stratified according to gender
- d. Stratified according to median years of education
- e. Stratified according to a clinical diagnosis of minor or major depression (for mobility and cognition)

3. Change in urinary severity index and depression category (based on the Geriatric Depression Scale) from baseline to 3 years. These analyses will be similar to the analyses for white matter hyperintensities in (1) and for mobility and cognition in (2), but using ordinal logistic regression.
 - a. According to treatment group (primary analysis)

$$\log(Y_{i1} > k / Y_{i1} \leq k) = \beta_{0k} + \beta_C x_i + \gamma_i$$

$$\log(Y_{i2} > k / Y_{i2} \leq k) = \beta_{0k} + \beta_C x_i + \beta_L + \beta_T x_i + \gamma_i$$

$$k = 1, \dots, m - 1$$

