Here, x_i is the treatment group indicator for participant i as in (1) and (2); Y_{i1} is the ordinal urinary severity index score for participant i at time 1 (baseline), which takes values from 1 to m ; Y_{i2} is the ordinal urinary severity index score for participant i at time 2 (36 month follow-up); β_{0k} is interpreted as the log odds of having ordinal urinary severity index score k at baseline in the reference group; β_C is interpreted as the log odds ratio for a one unit higher urinary severity index score at baseline between the intervention group and

the reference group, and will be zero if the two groups are exactly comparable in their baseline values; β_L is interpreted as the log odds ratio for a one unit higher urinary severity index score between the 36 month follow up and baseline in the reference group; β_T is interpreted as an interaction, the difference in log odds ratios for a one unit higher urinary severity index score between between the 36 month follow up and baseline and between the intervention group and the reference group and thus the parameter of primary interest; and γ_i is a random intercept for participant i that addresses the correlation in mobility across the two time points.

This analysis makes the proportional odds assumption which will be checked by software.

- b. Stratified according to < or > median age
 - c. Stratified according to gender
 - d. Stratified according to median years of education
 - e. Stratified according to a clinical diagnosis of minor or major depression
4. Change in markers of tissue damage associated with microvascular disease of the brain (via diffusion tensor imaging (DTI)) from baseline to 3 years. Change in DTI will be evaluated as it relates to:
- a. Treatment group (primary analysis)

$$\begin{aligned} Y_{i1} &= \beta_0 + \beta_C x_i + \gamma_i + \varepsilon_{i1} \\ Y_{i2} &= \beta_0 + \beta_C x_i + \beta_L + \beta_T x_i + \gamma_i + \varepsilon_{i1} \end{aligned} \quad (1.1)$$

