For mobility, cognition, and depression, variables are defined as in (1) with the following additions: δ_i is residual error in the model for change in WMH, and m_{i1} and m_{i2} are the values of WMH at baseline and follow-up, respectively. Some mediation measures of interest are as follows:

$$CDE = \beta_T$$

$$INT_{REF} = \theta_{INT} \alpha_0$$

$$INT_{MED} = \theta_{INT} \alpha_1$$

$$PIE = \theta_M \alpha_1$$

The controlled direct effect $CDE = \beta_T$ is the effect of treatment assignment in the absence of any WMH, $INT_{REF} = \theta_{INT} \alpha_0$ is the reference interaction between treatment assignment and WMH, $INT_{MED} = \theta_{INT} \alpha_1$ is the mediated interaction, and $PIE = \theta_M \alpha_1 x_i$ is the pure indirect effect. Combinations of these derived measures will be used to assess the degree of mediation, as described in VanderWeele. T.J. (2015). Explanation in Causal Inference: Methods for Mediation and Interaction, Oxford University Press. In particular, the proportion mediated is $\frac{INT_{REF} + INT_{MED} + PIE}{CDE + INT_{REF} + INT_{MED} + PIE}$.

Bootstrap standard errors and confidence intervals will be used for statistical inference, including estimation of standard errors and confidence intervals.

In secondary analyses, age, sex, and resultant ambulatory systolic BP at 36 months regardless of treatment assignment will be considered as mediators through similar methods. Specifically, age, sex, and systolic BP will replace $m_{i2} - m_{i1}$ in the model above and similar measures of interaction and mediation will be estimated.

7. Special Interest adverse events (falls, nervous system and vascular disorders) as related to numerous predictors of interest.

These outcomes are all count variables, so we use Poisson regression with each of the following predictors.

$$\log(\mu_i) = \log(n_i) + \beta_0 + \beta_1 x_i$$

Here μ_i is the count, n_i is the number of months in study, β_0 is the intercept with $\exp(\beta_0)$ interpreted as the rate of AE with mobility scale is zero, x_i is the predictor of interest, mobility scale and β_1 is the log rate ratio between groups and $\exp(\beta_1)$ is interpreted as the estimated ratio of rates for two subjects differing by one in their predictors of interest scale. This analysis will be repeated for the following predictors described below:

- a. Mobility variables
- b. Cognitive variables
- c. Treatment assignment
- d. Blood pressure
- e. Age
- f. Gender

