- g. Number of classes of antihypertensive medications
- h. A clinical diagnosis of minor or major depression
- i. Sleep scales and SF-36 (QOL)

A final multivariate model will include all significant predictors.

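### SAP item 7 models adverse-event counts by Poisson regression with no robust variance, dispersion parameter or dispersion check

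*SAP*

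**What the plan says.** SAP item 7 takes the counts of falls, nervous-system disorders and vascular disorders as outcomes and gives a single reason for its model: "These outcomes are all count variables, so we use Poisson regression with each of the following predictors". The equation is log(μ) = log(months in study) + β0 + β1x, with one predictor x at a time. The predictors are mobility and cognitive variables, "c. Treatment assignment", blood pressure, age, gender, number of antihypertensive classes, depression, and the sleep and SF-36 scales. Then: "A final multivariate model will include all significant predictors".

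The SAP supplies inferential detail for other items. Item 6 (mediation) says "Bootstrap standard errors and confidence intervals will be used for statistical inference", and item 3 (ordinal outcomes) says "This analysis makes the proportional odds assumption which will be checked by software". Item 7 has no counterpart to either. Protocol section 7.1 adds only a general screen for outliers and implausible values.

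**The concern.** A Poisson model sets the variance of each patient's count equal to its mean. The months offset corrects for unequal follow-up; it does not absorb differences between patients in their underlying event rate. If rates vary beyond the one predictor in the model, the rate ratio is still estimated consistently (given a correct mean model), but its model-based standard error is too small.

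Item 7 itself makes such variation plausible. It names nine groups of candidate predictors and fits them singly, so any that matter are left out of every other one-predictor model, including the treatment model.

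Two results depend on these standard errors. Item 7c is the SAP's only model-based comparison of these events between arms, and an interval that is too narrow could suggest a difference that is not there. The same p-values decide which predictors enter the final model.

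**Working it through.** **No figure to reproduce.** Item 7 states no event rate, sample size, power or significance level. Two-sided 5% is assumed below.

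**Inputs from the documents**
- 200 patients randomized 1:1, so 100 per arm (Protocol section 4).
- Follow-up of 36 months. On dropout, Protocol 4.3 says "we project a 3-year attrition rate of approximately 30" percent. I gave 30% of patients a follow-up uniform on 1 to 36 months and the rest 36 months.

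**Assumptions, because the documents are silent**
- Mean events per person over 36 months (m): 0.2, 0.5, 1 or 2.
- Log-normal person rates with log-rate SD (s): 0, 0.25, 0.5 or 1.0. A patient one SD above the median then has exp(s) = 1, 1.28, 1.65 or 2.72 times the median rate.

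**Step 1, approximation for full follow-up.** The variance-to-mean ratio is φ = 1 + m(exp(s²) − 1), and the true level of a nominal 5% Poisson test is 2[1 − Φ(1.96/√φ)].
- m = 0.2, s = 0.5: φ = 1 + 0.2 × 0.284 = 1.06; level 5.7%.
- m = 1, s = 0.5: φ = 1.28; level 8.4%.
- m = 1, s = 1.0: φ = 1 + 1.718 = 2.72; level 23%.
- m = 2, s = 1.0: φ = 1 + 2 × 1.718 = 4.44; level 35%.

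**Step 2, simulation of item 7c.** 20,000 trials per cell, with a two-group Poisson Wald test and exposure offset against the same estimate with sandwich variance. Shortened follow-up lowers the counts, so the results sit slightly below Step 1.

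False-positive rate at a true rate ratio of 1:

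| Mean events | Poisson, SD 0 | SD 0.25 | SD 0.5 | SD 1.0 |
|---|---|---|---|---|
| 0.2 | 4.5% | 4.7% | 5.0% | 8.0% |
| 0.5 | 4.8% | 5.1% | 6.5% | 13.6% |
| 1 | 5.1% | 5.7% | 7.7% | 21.4% |
| 2 | 4.9% | 6.4% | 11.4% | 33.0% |

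The sandwich variance gives 4.7-6.3% across all cells.

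Coverage of the nominal 95% interval at a true rate ratio of 1.5:

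| Mean events | Poisson, SD 0.5 | Poisson, SD 1.0 |
|---|---|---|
| 0.2 | 94.8% | 90.9% |
| 0.5 | 93.3% | 84.4% |
| 1 | 91.4% | 75.5% |
| 2 | 87.0% | 63.4% |

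Sandwich coverage is 93.7-95.1%.

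**Step 3, dependence on the log-normal shape.** With gamma-distributed rates instead (mean 0.5 to 2, gamma variance 0.5 to 2, 2,000 trials per setting), plain Poisson rejects in 8-35% of trials and sandwich in 5-7%.

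**Step 4, the significance screen.** The SAP gives no threshold; 5% is assumed. An unrelated standard-normal predictor in 200 patients passes with Poisson standard errors, at SD 0.5/1.0, in 5.6/8.5% (mean 0.2), 6.7/13.6% (0.5), 8.4/21.4% (1) and 11.2/32.0% (2) of trials. With sandwich errors it passes in 5.6-7.3%.

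On the size of the screen, item 2 lists four mobility measures ("gait speed, four stair ascent and descent time, supine to sit time", counting ascent and descent separately) and four cognitive ones. If item 7 uses these, adding treatment, blood pressure, age, gender, drug classes, depression, two sleep scales and SF-36 gives 4 + 4 + 9 = 17 predictors. Over three event groups that is at least 51 one-predictor models. The simulation covers one-predictor models only; the final model would absorb part of the excess variation.

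**The case against.** The strongest reply is that the harm is hypothetical. Item 7 does not prescribe model-based standard errors; it is silent. Neither document shows overdispersion, and the assumed ranges run from no inflation to 33% with nothing to place this trial between them. Eligibility also narrows the range of patients by excluding "History of stroke, dementia or clinically impaired gait". All of this stands and makes the size conditional. It does not remove the gap: a Poisson fit with no variance method named yields model-based errors, and patients can still differ on every predictor item 7 lists.

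The stakes are limited. The SAP introduces its list as added secondary analyses, and Protocol 5.7 also tabulates events by arm. That stands too, although a table carries no interval for the comparison.

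It could be said that the bootstrap sentence covers item 7. A participant-level bootstrap would indeed give valid errors, but the sentence sits inside item 6, before the item 7 heading.

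The screening problem is partly a separate one. Even exact 5% tests would pass about 51 × 0.05 = 2.6 predictors if none were related to events. Robust errors leave that untouched and remove only the excess above it.

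Finally, a Pearson-scaled (quasi-Poisson) variance works about as well in the treatment comparison: 5-7% in the overdispersed gamma scenarios. It is an acceptable alternative.

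**Conclusion.** The concern holds. The omission is definite; its consequence depends on dispersion that the documents do not give. If event rates vary appreciably between patients (log-rate SD 0.5 to 1.0) and events are not rare (mean of 1 to 2 per person), the 7c test runs at 8-33% instead of 5%, and its 95% interval covers in 63-91% of trials at a true rate ratio of 1.5. With rare events or little variation between patients, plain Poisson is adequate. Standard errors, intervals, p-values and the choice of predictors for the final model are affected. The change should be made because it is cheap and protects a between-arm safety comparison, but nothing here threatens the trial's main conclusions.

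**What to change.** State in item 7 that all its models, including 7c and the final model, are Poisson regressions with robust (sandwich) standard errors and the same log(months) offset, and that the 7c rate ratio with its robust interval is the between-arm comparison of these events.

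The cost is one SAP sentence and one software option, with no new data.
- **If Poisson holds:** the 7c standard error changes by about 1%. Power for a rate ratio of 1.5 is 24.3, 54.3, 83.4 and 98.5% with Poisson against 24.8, 55.0, 83.5 and 98.5% with robust errors (means 0.2, 0.5, 1 and 2).
- **If counts are overdispersed (SD 0.5 to 1.0):** standard errors, and so intervals on the log scale, widen by about 2-11%, 5-29%, 11-53% and 22-93% at the same means. Power for a rate ratio of 1.5 falls, for example from 72% to 44% at mean 1 and SD 1.0, and from 53% to 34% at mean 0.5 and SD 1.0. The higher figures come from tests that do not hold their 5% level.
- **A limit:** for continuous predictors in 200 patients the sandwich test runs at about 6-7%. That is slightly worse than plain Poisson when events are rare (mean 0.2, SD 0.5 or less: about 7% against 5-6%).
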